5.4.3.2 Pregnancies in Female Partners of Male Patients

Male patients will be instructed through the Informed Consent Form to immediately inform the investigator if their partner becomes pregnant while receiving chemotherapy study treatment (i.e., carboplatin and etoposide) or within 90 days after the final dose of tiragolumab or placebo, or 6 months after the final dose of chemotherapy study treatment, whichever is later. The investigator should report the pregnancy on the paper Clinical Trial Pregnancy Reporting Form and submit the form to the Sponsor or its designee immediately (i.e., no more than 24 hours after learning of the pregnancy), either by faxing or by scanning and emailing the form using the fax number or email address provided to investigators. Attempts should be made to collect and report details of the course and outcome of any pregnancy in the partner of a male patient exposed to study treatment. When permitted by the site, the pregnant partner would need to sign an Authorization for Use and Disclosure of Pregnancy Health Information to allow for follow-up on her pregnancy. If the authorization has been signed, the investigator should submit a Clinical Trial Pregnancy Reporting Form with additional information on the pregnant partner and the course and outcome of the pregnancy as it becomes available. An investigator who is contacted by the male patient or his pregnant partner may provide information on the risks of the pregnancy and the possible effects on the fetus, to support an informed decision in cooperation with the treating physician and/or obstetrician.

5.4.3.3 Abortions

A spontaneous abortion should be classified as a serious adverse event (as the Sponsor considers abortions to be medically significant), recorded on the Adverse Event eCRF, and reported to the Sponsor immediately (i.e., no more than 24 hours after learning of the event; see Section [5.4.2](#)).

If a therapeutic or elective abortion was performed because of an underlying maternal or embryofetal toxicity, the toxicity should be classified as a serious adverse event, recorded on the Adverse Event eCRF, and reported to the Sponsor immediately (i.e., no more than 24 hours after learning of the event; see Section [5.4.2](#)). A therapeutic or elective abortion performed for reasons other than an underlying maternal or embryofetal toxicity is not considered an adverse event.

All abortions should be reported as pregnancy outcomes on the paper Clinical Trial Pregnancy Reporting Form.

5.4.3.4 Congenital Anomalies/Birth Defects

Any congenital anomaly/birth defect in a child born to a female patient exposed to study treatment or the female partner of a male patient exposed to study treatment should be classified as a serious adverse event, recorded on the Adverse Event eCRF, and reported to the Sponsor immediately (i.e., no more than 24 hours after learning of the event; see Section [5.4.2](#)).

5.5 FOLLOW-UP OF PATIENTS AFTER ADVERSE EVENTS

5.5.1 Investigator Follow-Up

The investigator should follow each adverse event until the event has resolved to baseline grade or better, the event is assessed as stable by the investigator, the patient is lost to follow-up, or the patient withdraws consent. Every effort should be made to follow all serious adverse events considered to be related to study treatment or trial-related procedures until a final outcome can be reported.

During the study period, resolution of adverse events (with dates) should be documented on the Adverse Event eCRF and in the patient's medical record to facilitate source data verification.

All pregnancies reported during the study should be followed until pregnancy outcome.

5.5.2 Sponsor Follow-Up

For serious adverse events, adverse events of special interest, and pregnancies, the Sponsor or a designee may follow up by telephone, fax, email, and/or a monitoring visit to obtain additional case details and outcome information (e.g., from hospital discharge summaries, consultant reports, autopsy reports) in order to perform an independent medical assessment of the reported case.

5.6 ADVERSE EVENTS THAT OCCUR AFTER THE ADVERSE EVENT REPORTING PERIOD

After the end of the reporting period for serious adverse events and adverse events of special interest (as defined in Section 5.3.1), all deaths, regardless of cause, should be reported through use of the Long-Term Survival Follow-Up eCRF.

In addition, if the investigator becomes aware of a serious adverse event that is believed to be related to prior exposure to study treatment, the event should be reported through use of the Adverse Event eCRF. However, if the EDC system is not available, the investigator should report these events directly to the Sponsor or its designee, either by faxing or by scanning and emailing the paper Clinical Trial Serious Adverse Event/Adverse Event of Special Interest Reporting Form using the fax number or email address provided to investigators.

5.7 EXPEDITED REPORTING TO HEALTH AUTHORITIES, INVESTIGATORS, INSTITUTIONAL REVIEW BOARDS, AND ETHICS COMMITTEES

The Sponsor will promptly evaluate all serious adverse events and adverse events of special interest against cumulative product experience to identify and expeditiously communicate possible new safety findings to investigators, IRBs, ECs, and applicable health authorities based on applicable legislation.

The Sponsor has a legal responsibility to notify regulatory authorities about the safety of a study treatment under clinical investigation. The Sponsor will comply with regulatory requirements for expedited safety reporting to regulatory authorities (which includes the use of applicable systems, such as EudraVigilance), IRBs, ECs, and investigators.

To determine reporting requirements for single adverse event cases, the Sponsor will assess the expectedness of these events through use of the reference safety information in the documents listed below:

Drug	Document
Tiragolumab	Tiragolumab Investigator's Brochure
Atezolizumab	Atezolizumab Investigator's Brochure

The Sponsor will compare the severity of each event and the cumulative event frequency reported for the study with the severity and frequency reported in the applicable reference document.

Reporting requirements will also be based on the investigator's assessment of causality and seriousness, with allowance for upgrading by the Sponsor as needed.

An iDMC will monitor safety data during the study. An aggregate report of any clinically relevant imbalances that do not favor the test product will be submitted to health authorities.

6. STATISTICAL CONSIDERATIONS AND ANALYSIS PLAN

This is a Phase III, randomized, double-blind, placebo-controlled, multicenter study designed to evaluate the efficacy and safety of tiragolumab plus atezolizumab and CE compared to placebo plus atezolizumab and CE as 1L treatment in patients with chemotherapy-naïve ES-SCLC. The study is not powered to demonstrate statistical significance in terms of efficacy, and no formal hypothesis testing will be performed. More details of the analyses will be provided in the Statistical Analysis Plan (SAP).

The analyses of PFS and OS will be performed in the PAS and the FAS. Patients will be grouped according to the treatment assigned at randomization, regardless of whether they receive any assigned study drug. Confirmed ORR will be analyzed in patients within the PAS and the FAS who have measurable disease at baseline. DOR will be assessed in patients who have a confirmed objective response in the PAS and the FAS. TTCD analyses, mean scores and mean change from baseline analysis on PROs will be performed in the PAS and the FAS.

Safety analyses will be conducted in all randomized patients who received at least one dose of study treatment. Safety analyses will be performed by treatment arm and will be based on actual treatment received. Specifically, a patient will be included in the tiragolumab plus atezolizumab arm in the safety analyses if the patient receives any amount of tiragolumab, regardless of the initial treatment assignment at randomization.

6.1 DETERMINATION OF SAMPLE SIZE

The primary objective of this study is to enroll approximately █ patients in the PAS in order to characterize the efficacy profile of tiragolumab plus atezolizumab. Assuming a 15% prevalence of presence or history of brain metastases at baseline, approximately 128 patients in total will be randomized in this study.

6.1.1 Co-Primary Endpoint: Progression-Free Survival in the Primary Analysis Set

The primary analysis of the co-primary endpoint of PFS will be conducted at the time of the OS primary analysis when approximately █ deaths in the PAS have been observed. The expected time of analysis can refer to Section 6.1.2. At the time of the primary analysis of PFS, it is estimated that approximately █ PFS events (█ patients) would have been observed in the PAS; the exact number of PFS events will be determined at the time of OS primary analysis.

- PFS curve following one-piece exponential distributions
- Median PFS of [REDACTED] months in Arm A and [REDACTED] months Arm B, corresponding to a target HR of [REDACTED]
- Dropout rate of [REDACTED] over 12 months for PFS

6.1.2 Co-Primary Endpoint: Overall Survival in the Primary Analysis Set

- OS curve following one-piece exponential distributions
- Median OS of [REDACTED] months for Arm A and [REDACTED] months for Arm B, corresponding to a target HR of [REDACTED]
- Dropout rate of [REDACTED] over 24 months for OS

6.2 SUMMARIES OF CONDUCT OF STUDY

Study enrollment, study drug administration, reasons for study drug discontinuation, and reasons for study termination will be summarized by treatment arm. Major protocol deviations, including major deviations of inclusion/exclusion criteria, will be reported and summarized by treatment arm.

6.3 SUMMARIES OF TREATMENT GROUP COMPARABILITY

Demographic characteristics, such as age, sex, race/ethnicity, and baseline disease characteristics (e.g., ECOG Performance Status) will be summarized by treatment arm. Descriptive statistics (mean, median, standard deviation, and range) will be presented for continuous data, and frequencies and percentages will be presented for categorical data, as appropriate.

Baseline measurements are the last available data obtained prior to the patient receiving the first dose of any component of protocol treatment.

6.4 EFFICACY ANALYSES

Unstratified analysis will be considered as primary results given the potential small sample size within each stratum. The stratified analysis will also be provided.

The stratification factors will be the same as the randomization stratification factors used for IxRS (ECOG Performance Status and LDH) and applied to all endpoints where stratification analyses are planned. Stratification factor(s) may be removed from the stratified analyses if there is risk of overstratification. Analyses based on stratification factors recorded on the eCRF will also be provided if considerable discrepancy is observed between IxRS and eCRF records.

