4.2 METHOD OF TREATMENT ASSIGNMENT AND BLINDING

4.2.1 Treatment Assignment

This is a Phase III, randomized, double-blind, placebo-controlled multicenter study. After written informed consent has been obtained and eligibility has been established, the study site will obtain the patient's identification number and treatment assignment from the interactive voice or web-based response system (IxRS).

Patients will be randomized to one of two treatment arms:

- Arm A: tiragolumab + atezolizumab + CE
- Arm B: placebo + atezolizumab + CE

Randomization will occur in a 1:1 ratio through use of a permuted-block randomization method to ensure that an approximately equal number of patients will be enrolled in each treatment arm within the baseline characteristics of the following stratification factors:

- ECOG Performance Status (0 vs. 1)
- LDH (\leq ULN vs. $>$ ULN)

Patients should receive their first dose of study drug on the day of randomization if possible. If this is not possible, the first dose should occur within 5 days after randomization.

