6.4.1 Co-Primary Efficacy Endpoints

The co-primary efficacy endpoints are PFS (as assessed by the investigator according to RECIST v1.1) and OS in the PAS.

PFS is defined as the time between the date of randomization and the date of first documented disease progression (as assessed by investigators according to RECIST v1.1) or death, whichever occurs first. Patients who have not experienced disease progression and have not died by the time of analysis will be censored at the time of the last tumor assessment. Patients with no post-baseline tumor assessment will be censored at the date of randomization.

OS is defined as the time between the date of randomization and death from any cause.

Data for patients who are not reported as having died by the date of analysis will be censored at the date when they were last known to be alive. Data for patients who do not have post-baseline information will be censored at the date of randomization.

PFS and OS will be compared between treatment arms with use of the unstratified log-rank test. The HR for PFS and OS will be estimated using both unstratified and stratified Cox proportional hazards model. The 95% CI for the HR will be provided.

[REDACTED]

The investigator-assessed PFS rates at 6 months and at 1 year and OS rates at 1 year, 18 months, and 2 years after randomization will be estimated using Kaplan-Meier methodology for each treatment arm, along with 95% CIs calculated using the standard error derived from Greenwood's formula. The 95% CI for the difference in PFS rates and OS rates between the two treatment arms will be estimated using the normal approximation method.

The timing of the final PFS analysis is described in Section 6.1.1 and the analysis timing for OS is described in Section 6.1.2.

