1.2.1 Treatment Assignment and Blinding

This is a Phase III, randomized, double-blind, placebo-controlled multicenter study. After written informed consent has been obtained and eligibility has been established, the study site will obtain the patient's identification number and treatment assignment from the interactive voice or web-based response system (IxRS).

Patients will be randomized to one of two treatment arms:

- Arm A: tiragolumab + atezolizumab + CE
- Arm B: placebo + atezolizumab + CE

Randomization will occur in a 1:1 ratio through use of a permuted-block randomization method to ensure that an approximately equal number of patients will be enrolled in

each treatment arm within the baseline characteristics of the following stratification factors:

- ECOG Performance Status (0 vs. 1)
- LDH (\leq ULN vs. $>$ ULN)

Patients should receive their first dose of study drug on the day of randomization if possible. If this is not possible, the first dose should occur within 5 days after randomization.

Study site personnel (with the exception of the unblinded pharmacist) and patients will be blinded to treatment assignment during the study. The Sponsor and its agents will also be blinded to treatment assignment, with the exception of individuals who require access to patient treatment assignments to fulfill their job roles during a clinical trial. These roles include the unblinding group responsible, clinical supply chain managers, sample handling staff, operational assay group personnel, IxRS service provider, and Independent Data Monitoring Committee (iDMC) members.

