5.3.2 Main Analytical Approach for Primary Endpoints

5.3.3 Handling of Missing Data

Patients who are lost to follow-up will be censored at the last date they were known to be alive for the primary analysis of OS. If >5% of patients are lost to follow-up for OS in either treatment arm, a sensitivity analysis will be performed for the comparisons between two treatment arms in which patients who are lost to follow-up will be considered as having died at the last date they were known to be alive.

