5.3.4 Sensitivity Analyses for Primary Endpoints

Sensitivity analyses of the primary endpoints will be performed to assess the impact of stratification. These analyses will follow the same analyses method as the primary endpoints with the exception that PFS and OS will be compared using a stratified log-rank test and the HR will be estimated from stratified Cox regression hazard model according to the protocol-defined stratification factors as entered in IxRS for the PAS (see also Section 5.3.2).

When the clinical effect is delayed by >20% of the median OS of the control group, a sensitivity analysis of OS may be performed using the weighted log-rank test based on the Rho-Gamma weight function family ([Fleming and Harrington, 1991](#)) or piece-wise linear weight functions ([Lin and Leon, 2017](#)) that weight more heavily on late events to account for the delayed clinical effect ([Fine, 2007](#)). In addition, hazard ratio estimates based on the corresponding Cox model ([Lin and Leon, 2017](#)) using the piece-wise linear weight functions may also be provided to enhance clinical interpretation of the treatment effect that varies over time.

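### Randomization is stratified by ECOG status and LDH but the primary PFS and OS results are not; if both factors are strongly prognostic, the primary result is mildly conservative (minor)

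*Protocol*

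**What the plan says.** Protocol 4.2.1 uses permuted blocks "to ensure that an approximately equal number of patients will be enrolled in each treatment arm within the baseline characteristics" of ECOG status and LDH, and SAP 1.2.1 repeats the scheme ("Randomization will occur in a 1:1 ratio through use of a permuted-block randomization method"). Protocol 1.1 lists poor performance status and LDH among poor prognostic factors. SAP 5.3.5.1 names ECOG status and LDH as prognostic baseline characteristics.

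For the analysis, Protocol 6.4 states: "Unstratified analysis will be considered as primary results given the potential small sample size within each stratum". It adds: "The stratified analysis will also be provided". Protocol 6.4.1 is specific about the test, "PFS and OS will be compared between treatment arms with use of the unstratified log-rank test", and the estimate, "The HR for PFS and OS will be estimated using both unstratified and stratified Cox proportional hazards model". SAP 5.3.4 places the stratified test and HR, using the IxRS factors, among the sensitivity analyses: "Sensitivity analyses of the primary endpoints will be performed to assess the impact of stratification". Protocol 6.4 also allows a stratification factor to be dropped if overstratification threatens.

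The body of SAP 5.3.2, "Main Analytical Approach for Primary Endpoints", is not visible in the public copy, and a block in Protocol 6.4.1 is blacked out. Protocol 6 and SAP 2 say that the study is not powered for efficacy and tests nothing formally. SAP 2 gives the purpose of the efficacy analyses as judging consistency with the global study.

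**The concern.** Blocking within strata makes the arms more alike on ECOG and LDH than simple randomization would. If those factors drive outcome, the treatment estimate varies less from trial to trial than an analysis that ignores them assumes. The reported standard error is then too large, and the interval covers more often than 95%.

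Separately, the hazard ratio is not collapsible. When prognostic factors are left out, the HR estimates a marginal quantity that lies, on average, nearer to 1 than the HR within strata.

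No significance claim depends on this. What matters is the HR and its interval, because they will be compared with the global study. The visible text does not say which type of HR enters that comparison or which type the global study reports. The SAP estimand (1.1.1, Table 2) names a hazard ratio without saying whether it is marginal or conditional.

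**Working it through.** **The plan's own figure.** There is no power or alpha figure to reproduce, and the PAS size is blacked out. From Protocol 6.1, 128 randomized with 15% brain metastases gives 128 × 0.85 = 108.8 expected in the PAS.

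**Inputs from the documents.** About 128 patients, 1:1 permuted blocks in four strata, accrual over about 13 months (SAP 3.1), and a control median OS of 12.3 months, borrowed from the atezolizumab arm of the earlier trial described in Protocol 1.2.

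**Assumed, because the documents are silent or blacked out.** Block size 4, ECOG 1 in 60%, LDH above normal in 50%, cutoff at 30 months, 5% dropout over 24 months, exponential survival, and a prognostic HR per factor of 1.0 to 3.0. Each patient enters the PAS with probability 0.85, since brain metastasis is not a randomization factor.

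**Expected stratum sizes.** ECOG 0: 108.8 × 0.40 × 0.50 = 21.8 at each LDH level. ECOG 1: 108.8 × 0.60 × 0.50 = 32.6 at each LDH level.

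**Simulation of OS in the PAS** (6,000 trials per row; simulation error about 0.3 points on null rejection). The within-stratum HR is 0.70, except that null rejection is at HR 1.

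| Prognostic HR per factor | Unstratified mean HR | Model SE / true SD | Null rejection | Rejection at 0.70, unstratified vs stratified |
|---|---|---|---|---|
| 1.0 | 0.702 | 0.242 / 0.244 | 5.1% | not tabulated |
| 1.5 | 0.706 | 0.242 / 0.233 | 4.7% | not tabulated |
| 2.0 | 0.722 | 0.242 / 0.226 | 3.7% | 25% vs 31% |
| 3.0 | 0.753 | 0.243 / 0.214 | 2.8% | 18% vs 31% |

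**Hand check of the 2.0 row.**
- SE ratio: 0.242 / 0.226 = 1.07, so the SE is 7% too large.
- Null rejection: at HR 1 the model SE is 0.230 and the true SD 0.217, so 2Φ(−1.96 × 0.230/0.217) = 2Φ(−2.08) = 3.8%.
- Unstratified rejection at 0.70: mean z = ln(0.722)/0.242 = −1.35, SD of z = 0.226/0.242 = 0.93, and Φ((−1.96 + 1.35)/0.93) ≈ 26%.
- Stratified rejection at 0.70: mean HR 0.698, SE 0.248, SD 0.246, so mean z = −1.45, SD of z = 0.99, and Φ((−1.96 + 1.45)/0.99) ≈ 30%.

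These agree with the simulation.

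**Other settings at 2.0.** A second simulation used ECOG 1 in 70%, LDH above normal in 55%, cutoffs of 24 and 32 months, no dropout, and both OS and PFS (control median PFS 5.2 months). It gave null rejection of 3.5-4.2%, an SE 4-7% too large and a mean HR of 0.71-0.73. At 1.5 it gave 4.8-4.9%, 1-3% and 0.70-0.71. A third simulation, at 30 months, gave an OS SE of 0.240 against 0.224 and rejection at 0.70 of 26% against 31%. The FAS shows the same pattern.

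**Do small strata harm the stratified analysis?** Across the prognostic strengths in the table, the stratified analysis had 94.8-95.6% coverage, a mean HR of 0.697-0.702 and null rejection of 5.0-5.5%. With ECOG 1 in 80%, the smaller strata hold 108.8 × 0.20 × 0.50 = 10.9 patients each, and null rejection at 2.0 was 5.3%. For PFS it was about 4.5-6%.

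**Cost of stratifying.** With non-prognostic factors and HR 1, the SE is 0.234 against 0.229 (2% larger). At 2.0 and HR 0.70 it is 0.248 against 0.242 (2.5% larger). Across settings the increase is about 2-4%.

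**Gap from comparing unlike HRs.** At 2.0 the average ratio is 0.722 / 0.698 = 1.034, about 3%.

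**The case against.** The choice is prespecified and explained, and stratified results are planned in both documents. There is no power claim and no formal test. The effect is clear only at a prognostic HR of about 2 per factor. Protocol 1.1 does not support that figure: it refers to poor performance status, while the trial enrols only ECOG 0 and 1. Stratifying does not narrow the interval. Since both HRs will be available, either type can be matched to the global study. All of this stands, and it is why the point is minor.

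It does not rescue the stated reason, because the stratified analysis behaves well at this size. Nor does it settle which HR will be used in the consistency comparison.

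A reader might go further and infer that the unstratified HR is biased or the primary analysis invalid. The documents and figures do not support that: it is a sound estimate of a marginal effect, and its error rate is below nominal, not above.

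A reader might also infer that covariate adjustment is absent from the plan. That cannot be charged, because the body of SAP 5.3.2 and part of Protocol 6.4.1 are not visible.

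Finally, a Cox model with ECOG and LDH as two covariates might look like the natural replacement. Its Wald test rejected 4.8-6.6% under the null across the simulations, mostly above 5%, so it is not clearly better than the stratified analysis already planned.

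**Conclusion.** The point holds as a minor one. The primary PFS and OS results leave out the two factors used to stratify randomization, which the documents treat as prognostic, and the small-strata reason has little force with about 109 patients in four strata.

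If each factor has a prognostic HR of about 2, the unstratified SE is 4-7% too large and null rejection is about 4%. The mean OS HR is about 0.72 against 0.70 within strata, and the rejection rate at HR 0.70 is about 26% against 31%. At 1.5 the effect is small (SE 1-4% too large, null rejection 4.7-4.9%), and at 1.0 it is nil.

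These sizes rest on the assumed prognostic strengths, factor frequencies, block size, cutoff and exponential survival. The shift towards 1 is an average, not a statement about any single data set.

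**What to change.** If the data are still blinded:
- In Protocol 6.4 and 6.4.1 and in the SAP (which supersedes the protocol for filing, SAP 5), make the planned stratified log-rank test and stratified Cox HR, using IxRS ECOG and LDH, the primary result. Keep the unstratified result as the sensitivity analysis.
- State in the SAP estimand (1.1.1, Table 2) that the HR is conditional on these two factors.
- Replace the open allowance to drop a factor with a rule fixed before unblinding, since it would now affect the primary result.

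If the data are already unblinded (Protocol Appendix 1 gives the cutoff as 31 August 2023; the documents do not state the unblinding status), leave the prespecified primary result as it is and show the stratified HR beside it.

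In either case, name the type of HR used to judge consistency with the global study and take the same type from both studies. A two-covariate Cox model is optional and supportive only; if it is added after unblinding, label it so.

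The cost is a few sentences and a change in the order of results already planned, with no new data. The statistical price is an SE about 2-4% larger, with no gain if the factors turn out not to be prognostic.
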